### 14.8 Body Weight and Body Mass Index

The listing of body weight assessment and BMI will include all the information collected. This listing will be presented by treatment group defined in Section 4.6, sorted by Participant ID and visit for the Safety Analysis Set.

Summary statistics for body weight and BMI in accordance with Section 4.2 will be presented for baseline and for each scheduled post baseline visit (which also includes the change from baseline). The summary table will be done for the Safety Analysis Set for treatment groups defined in Section 4.6.

The value of BMI that is recorded in the electronic data capture system will be sued for all listings and summary tables. BMI to be calculated using the height value recorded at screening.

## **15 PHARMACOKINETICS**

All PK analyses will be conducted on the plasma concentration data of palivizumab.

The individual subject listings of PK plasma concentrations will be presented for the Safety Analysis Set to include data for placebo subjects, while the summary of plasma concentrations will be based on the PK Analysis Set.

Individual and mean PK parameters and any outputs related to PK parameters (e.g., bioequivalence analysis) will be based on the Per Protocol PK Analysis Set.

Individual plasma concentration over time plots in linear and logarithmic scale will be presented for Full PK Analysis population. Mean plasma concentration over time plots will be presented for Per-protocol PK population.

## 15.1 Data Handing for PK Data

Plasma concentration values not collected or not determined will be treated as missing. The plasma concentrations that are below the limit of quantifiable (BLQ) will be designated a value of zero for the summary of concentration-time data, except for geometric mean, where they will be excluded from the calculation.

For individual and mean plasma concentration-time plots, BLQ values will be set to zero for linear plots and BLQ values will be excluded from presentation semi-logarithmic scale.

### 15.2 Summary Statistics for Plasma PK Concentration Data

Plasma concentrations of palivizumab will be used as supplied by the laboratory. The units of concentration and resulting PK parameters, with amount or concentration in the unit, will be presented as they are received from the laboratory.

The actual sampling date and time and elapsed time relative to dosing time for plasma data will be listed by Participant and nominal sampling time, with time deviation (difference in hours between nominal and actual sampling times) calculated. These results will also be listed by treatment group (Section 4.6), sorted by Participant ID and visit.

Summary statistics of PK concentration data of palivizumab (number of non-missing observation [n], arithmetic mean, standard deviation [SD], coefficient of variation [CV%], geometric mean, median, minimum and maximum) will be calculated for each time point and summarised by treatment group (Section 4.6).

When reporting individual values and descriptive statistics for palivizumab concentration data, the following rules will apply regarding rounding and precision:

- Descriptive statistics for PK concentration data will be reported to the same level of precision as the individual data for the minimum and maximum, and to 1 additional decimal place or 1 additional significant figure depending on the reporting format of the original data with a maximum of 3 significant figures for the mean (arithmetic and geometric), median and standard deviation.
- Between-Participant CV% will be reported as a percentage to 1 decimal place.

#### **15.3** Summary Statistics for Plasma PK Parameter

Calculated PK parameters will be listed and summarized descriptively, including number of non-missing observation (n), arithmetic mean, SD, minimum, median, maximum, coefficient of variation [CV(%)], geometric mean, geometric CV%.

When reporting individual values and descriptive statistics for PK plasma parameters data for palivizumab, the following rules will apply to rounding and precision:

- Individual values for PK parameters will be reported to 3 significant figures.
- Descriptive statistics for PK parameters will be reported to 3 significant figures.
- Between-Participant CV% and geometric CV% will be reported as a percentage to 1 decimal place.
- Missing data will not be imputed.

### **15.4** Concentration-Time Profiles

Individual plasma concentrations of palivizumab over actual time will be plotted with the concentration result (y-axis) displayed for the Full PK Analysis population on a linear scale and on a logarithmic scale.

Mean plasma concentrations of palivizumab over scheduled time will be plotted with the concentration result (y-axis) displayed for the Per-protocol PK Analysis population on a linear scale and on a logarithmic scale.

#### **15.5** Plasma PK Parameters

For PK analysis, the PK samples from pre-dose to Day 99 will be considered. Actual sampling times will be used for the PK analysis, with the exception of pre-dose data which will be given the nominal time of 0.00 hr. If the actual sampling time is not recorded, the nominal sampling time will be used.

The plasma concentrations below the limit of quantifiable (BLQ) values will be treated as 0 for PK analysis.

The following PK parameters will, where possible be determined from the plasma concentration of palivizumab by non-compartmental analysis using Phoenix WinNonlin® software (version 8.3 or higher).

Parameter	Definition
C max	Individual maximum concentration (C max ) values are directly determined
	from the plasma concentration time profiles for each Participant.
C 29days	Individual concentration values on Day 29±1 directly determined from the
	plasma concentration time profiles for each Participant.
C 57days	Individual concentration values on Day 57±3 directly determined from the
	plasma concentration time profiles for each Participant.
T max	The time to attain maximum concentration. If the same C max concentration
	occurs at different time points, T max is assigned to the first occurrence of
	C max .
AUC 0-last	The area under the curve spanning time interval from time zero to the last
	time point with measurable concentration using the linear trapezoidal rule.
AUC0-168h	The area under the curve spanning time interval from time zero up to 168h
	post dose using the linear trapezoidal rule
AUC 29days	The area under the curve spanning time interval from time zero up to
	Day 29±1 post dose using the linear trapezoidal rule
AUC 57days	The area under the curve spanning time interval from time zero up to
	Day 57±3 post dose using the linear trapezoidal rule

CONFIDENTIAL

AUC 0-inf	The area under the plasma concentration-time curve over the time interval
	from time 0 extrapolated to infinity ( $\infty$ ) using the following formula
	$AUC_{0-\infty} = AUC_{0-t} + \frac{C_t}{\lambda_{\infty}}$
	Where, C't is the predicted concentration at the time t (last time point with a
	measurable plasma concentration above the quantification limit) at which
	quantification was still possible, the calculation of $\lambda z$ or kel is given below.
AUC%extrap	The percentage of the AUC that has been extrapolated beyond the last
	observed data point, using the following formula
	$AUC_{\%extrap} = \left(\frac{AUC_{0-\infty} - AUC_{0-t}}{AUC_{0-t}}\right) * 100$
$\lambda z$ or $K_{el}$	The apparent terminal elimination rate constant will be estimated from a
	regression of ln(C) versus time over the terminal log-linear drug disposition
	portion of the concentration-time profiles.
t1/2	The terminal half-life will be calculated from the terminal rate constant using
	the equation:
	$T_{1/2} = \frac{Ln(2)}{\lambda_z}$
CL/F	Apparent total plasma clearance will be calculated as following equation:
	$CL/F = \frac{D}{AUC_{0-\infty}}$
	Where $D = Administered$ dose; $AUC_{0-\infty} = AUC_{0-inf}$
Vz/F	Apparent terminal volume of distribution will be calculated according to the
	following equation:
	$V_z/F = \frac{CL/F}{\lambda_z}$
	$\lambda_z = \lambda_z$

The following will be considered for reporting the PK parameters:

- The PK parameters which are not determined from PK analyses due to inadequate concentration data or missing data will be considered as 'not estimable (NE)'.
- No value of  $\lambda_z$  or Kel, CL/F and Vz/F, AUC0-inf, and  $t_{1/2}$  will be reported for cases that do not exhibit a terminal log-linear phase in the concentration versus time profile. Criteria which may indicate a failure to exhibit a terminal log-linear phase in the concentration-versus-time profile include:
  - Positive slope for log regression fit
  - $\circ$  radj < 0.75
  - Time points in the interval used in estimating the half-life span less than one half-life
  - $_{\odot}$   $\,$  Fewer than 3 points with measurable concentration after  $T_{max}$
- Profiles which meet any of the above criteria will be reviewed on a case-by-case basis. Any variations from the above criteria will be noted as a comment in the data file of parameters.

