### 4.5 Handling of Missing Data

In general, all data will be analysed as collected and missing values will not be imputed or replaced unless stated otherwise.

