### 15.7 Bioequivalence Analysis

The bioequivalence analysis will be conducted for  $C_{max}$ , AUC0-inf and AUC0-last. Additionally, the bioequivalence analysis will also be conducted for concentrations collected on Days 29±1 day and 57±3 days as well as for partial AUC up to 168 hours, Days 29±1 day and 57±3. Natural log-transformed PK parameter  $C_{max}$ , C29days, C57days, AUC0-last and AUC0-inf, AUC0-168h, and AUC up to Days 29 and 57 will be analysed using the general linear model with the treatment as fixed via PROC GLM in SAS. For the purpose of the analysis, a preliminary ANCOVA model including variables group, age, sex, BMI and weight will be performed. If variables age, sex, BMI or weight were to be significant in this analysis, these variables will be kept in the final analysis. Upon review of the immunogenicity analysis, secondary ANCOVA analysis including ADA as a categorical or numerical variable could be performed. The 90% confidence intervals of the geometric least square mean ratio of test and reference i.e., MB05 group means relative to the EU-Synagis group means will be obtained by back transformation.

The following comparisons will be done:

(1) MB05 as Test VS EU-Synagis® as Reference

(2) MB05 as Test VS US-Synagis® as Reference

(3) EU-Synagis® as Test VS US-Synagis® as Reference

Bioequivalence will be concluded for  $C_{max}$ ,  $AUC_{0-last}$ ,  $AUC_{0-inf}$  and additional parameters  $C_{29days}$ ,  $C_{57days}$  and partial areas  $AUC_{0-168h}$ ,  $AUC_{29days}$  and  $AUC_{57days}$  between test and refere, if the 90% CIs for the ratio of geometric least squares means are contained within the range 80.00% to 125.00%. However, for  $C_{max}$ , a wider range 70.00% to 143.00% could also be considered.

Protocol Number: MB05-A-01-21 Document Status: Final 2.0 Version date: 15-Jun-2023

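### BLQ values set to 0 and then log-transformed are deleted from the C29days and C57days bioequivalence tests, which favours equivalence if one product is lost faster

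*SAP*

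**What the plan says.** - **BLQ rule for parameters (SAP 15.5).** "The plasma concentrations below the limit of quantifiable (BLQ) values will be treated as 0 for PK analysis".
- **Definition of the late concentrations (SAP 15.5).** The parameter table defines C57days as "Individual concentration values on Day 57±3 directly determined from the" participant's profile. C29days is defined in the same way. Neither is modelled or extrapolated.
- **Use in the bioequivalence analysis (SAP 15.7).** "Additionally, the bioequivalence analysis will also be conducted for concentrations collected on Days 29±1 day and 57±3 days". The response is the "Natural log-transformed PK parameter", and the listed parameters "will be analysed using the general linear model with the treatment as fixed via PROC GLM in SAS". The section then says that bioequivalence will be concluded for C29days and C57days if the 90% CI lies within 80.00% to 125.00%.
- **Missing data.** SAP 4.5 says that "missing values will not be imputed or replaced unless stated otherwise". SAP 15.3 says of the PK parameters: "Missing data will not be imputed".
- **The other BLQ rule (SAP 15.1).** In concentration summaries BLQ counts as zero, "except for geometric mean, where they will be excluded from the calculation". This governs tables of concentrations by time point. It does not govern the bioequivalence model.

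Neither document gives a lower limit of quantification (LLOQ), an expected BLQ proportion, or a CV for the Day 29 or Day 57 concentration.

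**The concern.** A late concentration is compared between products because it can reveal that one of them is lost faster. Under these rules, a participant who has already fallen below the LLOQ has a parameter value of 0. Its logarithm is undefined, so the record becomes a missing response and PROC GLM omits it. The SAP does not say this in words; it follows from setting BLQ to 0 and then taking logs.

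The deletion depends on the outcome, since it removes the lowest values and no others. If one product clears faster, more of its low values go, the remaining geometric means move closer together, and the ratio shifts towards 1. In an equivalence test that is the anti-conservative direction. The SAP attaches a formal conclusion to these two parameters, so they are not merely descriptive. It also allows a secondary model with anti-drug antibody (ADA) status; anyone BLQ on Day 57 would be missing from that model for C57days as well.

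**Working it through.** **1. Path of one BLQ sample.** Day 57 sample BLQ → C57days = 0 (SAP 15.5) → ln(0) undefined (SAP 15.7) → missing response → omitted from PROC GLM. No substitution value, censored-data model or count of exclusions appears in SAP 15.1 or 15.5 to 15.7, and imputation is ruled out (SAP 4.5, 15.3).

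**2. The plan's own figure.** SAP section 3 gives CV 0.35, true ratio 1, 45 per arm, 90% CI and about 85% power. The margin comes from SAP 15.7.

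- Log-scale SD: s = √ln(1 + 0.35²) = 0.340.
- Standard error: 0.340 × √(2/45) = 0.0717.
- Normal approximation: 2Φ(0.2231/0.0717 − 1.645) − 1 = 85.8%. The exact calculation with the t distribution gives 85.2%.

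The stated power reproduces, so the same set-up is used below. The CV is stated for AUC and Cmax; applying it to C57days is an assumption.

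**3. Effect of deletion on the ratio.** Suppose a share p of the reference arm is BLQ, and the true test/reference ratio is 0.80.

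- Standardised LLOQ in the reference arm: a = Φ⁻¹(p).
- In the test arm: a′ = a + 0.2231/s.
- Mean log of the retained values rises by s × λ, where λ(a) = φ(a)/(1 − Φ(a)).
- Observed ratio: 0.80 × exp{s[λ(a′) − λ(a)]}.

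For p = 5% and s = 0.340: a = −1.645 and λ = 0.109; a′ = −0.988 and λ = 0.292. The ratio is 0.80 × exp(0.340 × 0.183) = 0.851.

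**4. False passes.** These come from simulation with 20,000 runs, 45 per arm, true ratio 0.80 and BLQ values deleted. BLQ shares and the log-SD of 0.6 are assumptions.

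| BLQ, reference arm | BLQ, test arm (s = 0.340) | Observed ratio (s = 0.340) | False pass (s = 0.340) | Observed ratio (log-SD 0.6) | False pass (log-SD 0.6) |
|---|---|---|---|---|---|
| 0% | 0% | 0.800 | 4.9% | 0.800 | 1.9% |
| 1% | 4.8% | 0.821 | 10.6% | 0.816 | 3.6% |
| 5% | 16.2% | 0.851 | 24.3% | 0.844 | 7.9% |
| 10% | 26.6% | 0.872 | 38.7% | 0.863 | 11.8% |

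At log-SD 0.8 the test almost never passes with 45 per arm: at most 0.4% over the same BLQ range.

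**5. How likely BLQ is.** With median C57days equal to K times the LLOQ, P(BLQ) = Φ(−ln K / SD).

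| K | SD 0.34 | SD 0.6 | SD 1.0 |
|---|---|---|---|
| 2 | 2.1% | 12.4% | 24.4% |
| 5 | about 0% | 0.4% | 5.4% |
| 10 | about 0% | about 0% | 1.1% |

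The documents do not fix K.

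**The case against.** Four points on the other side have weight.

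**No BLQ value is shown at these visits.** A reader might infer that participants will be lost from these tests. The documents do not support that. Sampling runs to Day 99 and AUC0-inf is a primary parameter, so measurable concentrations are evidently expected well after Day 57. This stands: the point is conditional.

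**Large BLQ shares are hard to reach.** If the Day 57 geometric mean were 3 µg/mL and the LLOQ 0.1 to 0.5 µg/mL (assumptions), the mean would be 6 to 30 times the LLOQ. A single log-normal population would then need a log-SD of ln 6/1.555 = 1.15 to ln 30/1.555 = 2.19 to give 6% BLQ. Otherwise there would have to be a rapidly clearing subgroup, which the documents do not quantify. Likewise, the rows in step 4 at s = 0.340 need a median of only 2.2, 1.75 or 1.55 times the LLOQ. This also stands: those figures show sensitivity and do not forecast what will happen.

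**The parameters are additional.** A reader might extend the point to the primary conclusion. That fails: Cmax is a positive value, AUC0-inf builds on the last measurable concentration, and a BLQ sample counted as 0 still leaves a positive partial AUC. Participants who clear early therefore stay in the tests of AUC29days and AUC57days, and SAP 17 permits exploring CL/F and AUC0-inf against ADA status. Faster loss would not go unseen. Also, the SAP 15.1 exclusion is only a table convention, and BLQ values remain visible in the listings and the other statistics.

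**Keeping BLQ values has a price.** A left-censored log-normal model was simulated with truly equal products, 47 per arm, CV 0.35 among the other participants, geometric mean 3 µg/mL and 2 versus 2 BLQ. The pass rate fell from about 88–89% to 0% at LLOQ 0.1, and from 86% to 52–53% at LLOQ 0.5. At LLOQ 0.1 the fitted SD rose from 0.33 to 0.79, so the CI half-width alone, 1.645 × 0.79 × √(2/47) = 0.268, exceeds ln 1.25 = 0.223. This stands, and it argues against making such a model the sole analysis.

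None of this answers the rule itself. If anyone is BLQ, the deletion is selective, it is not announced, and a bioequivalence conclusion is drawn from what remains.

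**Conclusion.** The point holds in conditional form. As written, the SAP deletes any participant who is BLQ on Day 29 or Day 57 from the test of that concentration, and does so because the value is low. If one product is lost faster, the bias favours a bioequivalence conclusion.

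The size cannot be fixed from the documents. It is zero if nobody is BLQ, which is most plausible at Day 29. With a log-SD near 0.34 and a median close to the LLOQ, even 1% BLQ in the reference arm roughly doubles the false-pass rate at a true ratio of 0.80 (4.9% to 10.6%). With a log-SD of 0.6, the rate passes the nominal 5% somewhere between 1% and 5% BLQ (3.6% and 7.9%). The consequence is confined to C29days and C57days.

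**What to change.** Amend SAP 15.5 and 15.7 before unblinding, so that the treatment of zeros is not chosen after seeing which arm has them:

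1. Among the PK parameters, keep BLQ = 0 for AUC only.
2. State that the PROC GLM result for C29days and C57days covers participants with quantifiable values.
3. Report the number BLQ per arm beside each ratio and each geometric mean.
4. If any participant is BLQ, run one pre-specified sensitivity analysis that keeps them: BLQ set to LLOQ/2, or left-censored at the LLOQ. Choose which in advance.
5. Do not conclude bioequivalence for that parameter from the quantifiable-only analysis alone.

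The cost is SAP wording, two extra counts in the outputs and, only if needed, one more model. No new data are required. The downside is that a few BLQ values inflate the variance, so the sensitivity analysis can fail even when the products are equal. It should be read together with the BLQ counts, and a failure with balanced counts should not by itself be taken as evidence of a difference.

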6.7.2 Secondary Endpoints

### **Pharmacokinetics**

Additional PK parameters to be determined include (but are not limited to):

- Time to Cmax (Tmax)
- Apparent terminal elimination half-life  $(t_{1/2})$
- Apparent volume of distribution (Vz/F)
- Apparent total serum clearance (CL/F)
- Area under the serum concentration-time curve from time zero to time t (AUCt)

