### 5.3 Per Protocol Pharmacokinetic Analysis Set

The per protocol pharmacokinetic analysis set will include all subjects in the PK Analysis Set who have no major protocol violations that impact on pharmacokinetics. Subjects who do not complete the sampling per schedule but have sufficient data points to construct each concentration-time profile will be considered PK evaluable.

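### AUC0-last is tested for bioequivalence with no common end time or minimum last sampling day, so early leavers can enter this secondary comparison with truncated areas

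*SAP*

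**What the plan says.** Protocol 6.7.2 lists as a secondary endpoint the "Area under the serum concentration-time curve from time zero to time t", and does not define t. SAP 15.5 makes this AUC0-last: "The area under the curve spanning time interval from time zero to the last" time point with a measurable concentration, by the linear trapezoidal rule. It states that "the PK samples from pre-dose to Day 99 will be considered", but sets no end time that every participant must reach.

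SAP 5.3 defines the Per Protocol PK set: "Subjects who do not complete the sampling per schedule but have sufficient data points to construct each concentration-time profile will be considered PK evaluable". SAP 15 bases all bioequivalence outputs on that set. SAP 15.7 applies the 80.00–125.00% criterion to AUC0-last alongside Cmax and AUC0-inf. It then extends the test: "Additionally, the bioequivalence analysis will also be conducted for concentrations collected on Days 29±1 day and 57±3 days as well as for partial AUC" to 168 hours, Day 29 and Day 57.

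The two later partial areas run up to "Day 29±1 post dose using the linear trapezoidal rule" and "Day 57±3 post dose using the linear trapezoidal rule". SAP 15.5 also says "Actual sampling times will be used for the PK analysis". Only AUC0-168h has its end point given in hours.

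SAP 4.5 rules out imputation in general. Protocol 7.4 asks that, at withdrawal, only the samples due that day be attempted.

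**The concern.** In a parallel design each participant supplies one area, and the ratio compares areas between different people. That is a comparison of exposure only if the areas cover the same interval. When concentrations fall below quantification, AUC0-last stops early for a pharmacokinetic reason and little area is lost. When a participant leaves, it stops for an administrative reason and a large part of the area may be missing.

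The SAP does not separate the two cases. A participant last sampled at Day 29 has a 28-day area, which is set against 98-day areas. The truncated values widen the spread. If leavers are unevenly divided, they also move the ratio in that trial. What is at stake is a secondary bioequivalence conclusion that could be harder to reach, or shifted, because of when people left.

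A smaller point of the same kind concerns AUC29days and AUC57days. If they end at the actual visit, two participants' intervals can differ by up to 2 and 6 days.

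**Working it through.** **Inputs from the documents.** SAP 3: CV 0.35, 90% CI, true ratio 1, 45 evaluable and 47 enrolled per arm, 5% dropout, about 85% power. SAP 15.7: limits 80.00–125.00%. Protocol Appendix 2: 168 h is Day 8, so Day d is d − 1 days after dosing. Day 15, 29, 57 and 99 are therefore 14, 28, 56 and 98 days.

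**Assumptions not in the documents.** One-compartment IM profile, C(t) proportional to e^(−kt) − e^(−ka·t), with ka 0.6/day and half-life 18–28 days.

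**1. The plan's own power.**
- Log-scale SD = √ln(1 + 0.35²) = 0.340.
- With 45 per arm, SE = 0.340 × √(2/45) = 0.0717.
- Approximate power = 2Φ(0.2231/0.0717 − 1.662) − 1 = 2Φ(1.45) − 1 = 0.853. The exact calculation gives 85.15%, so the stated 85% is reproduced.
- With 47 complete per arm, exact power is 87.0%.

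**2. Share of the 98-day area kept by a leaver.**

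| Last sample | Half-life 18 d | 24 d | 28 d |
|---|---|---|---|
| Day 15 | 0.386 | 0.319 | 0.289 |
| Day 29 | 0.652 | 0.567 | 0.527 |

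A second calculation used ka 0.5/day, the protocol's sampling days, the linear trapezoid and half-lives of 15–30 days. It gave 50–70% at Day 29 and 80–93% at Day 57.

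**3. Shift of the ratio, two leavers in one arm and none in the other, 47 per arm.** Shift = exp((2/47) × ln r) − 1, where r is the share kept.
- Day 29: r = 0.652 gives −1.8%; r = 0.527 gives −2.7%.
- Day 15: r = 0.386 gives −4.0%; r = 0.289 gives −5.1%.

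**4. Power.** The fair comparison starts from 47 enrolled and sets truncated values kept in against the same values removed. The kept-in column comes from 200,000 simulated trials per row (log-SD 0.340, ratio 1, ln r added to each leaver, mid-range r of 0.58 for Day 29 and 0.35 for Day 15). The removed column is exact.

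| Leavers | Kept in | Removed | Gain (points) |
|---|---|---|---|
| 2 v 2, Day 29 | 84.6% | 85.2% (45/45) | 0.6 |
| 2 v 0, Day 29 | 83.6% | 86.1% (45/47) | 2.5 |
| 2 v 2, Day 15 | 77.5% | 85.2% | 7.7 |
| 2 v 0, Day 15 | 74.1% | 86.1% | 12.0 |

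Over half-lives of 18–28 days the four gains range from −0.5 to 1.5, 1.1 to 3.7, 5.9 to 12.3 and 9.5 to 17.1 points. For Day 57 leavers (r = 0.83) keeping them gives 86.8% (2 v 2) or 86.6% (2 v 0), slightly more than removing them.

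**5. Visit windows.** ±1 day changes AUC29days, and ±3 days changes AUC57days, by at most about 3% under either set of assumptions. Uniform ±3% noise has SD 0.03/√3 = 0.0173. The log-SD becomes √(0.340² + 0.0173²) = 0.3404, and power stays at about 85%.

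**The case against.** **Existing safeguards.** SAP 5.3 excludes major violations that affect PK. Protocol 7.4 counts three consecutive missed visits as major noncompliance. SAP 8 has deviations assessed before lock and unblinding, SAP 15.5 allows a parameter to be reported as not estimable when data are inadequate, and SAP 19.2 has the populations approved before unblinding. A Day 15 leaver might well be excluded under these rules. That stands in part: exclusion is possible, but nothing requires it. AUC0-last can be computed from any truncated profile, the specific criteria in SAP 15.5 concern only the terminal-phase parameters, and no rule names a last sampling day.

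**AUC0-last is customary.** This stands. The protocol leaves t open, and the SAP's AUC0-inf entry takes t as the last measurable time. A reader might infer a departure from the protocol endpoint, but the documents do not show one. The gap is the missing completeness rule when the parameter is tested.

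**Planned power.** A reader might infer that ordinary dropout pulls power well below 85%. That would take the 5% out of the 45 who already remain after dropout, and compare with a trial without leavers. Removing the values loses those participants too. Counted from 47, the Day 29 difference is small.

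**Bias.** A reader might also infer a systematic bias between products. The trial is randomised and double-blind, and nothing in the documents suggests that leaving depends on arm. Chance imbalance has zero expected bias, though it can shift the ratio in the one trial that is run. With independent 5% dropout from 47 per arm, a given pair of arms differs by two or more leavers with probability about 47%, counting leavers at any time.

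**Visit windows.** The ± may only name the visit, and interpolation to a fixed time is not excluded. This stands: the end time needs stating, but no error is shown.

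**Conclusion.** The concern holds at limited size. As written, the SAP lets a participant who left around Day 29 or earlier enter the AUC0-last test with a substantially truncated area.

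The effect is mainly noise, plus a chance shift of about 2–5% under a two-to-none split. The power at stake is small for Day 29 leavers, material for Day 15 leavers, and negligible from Day 57 on. The documents give no timing of dropout, so how many participants leave early enough to matter is unknown. The sizes also depend on the assumed ka and half-life, CV 0.35 and a true ratio of 1.

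It would be wrong to read this as a threat to the primary conclusion. Those endpoints are AUC0-inf, whose tail is extrapolated, and Cmax; neither is cut off in this way. The change is worth making because it is cheap and takes an undefined judgement out of a tested parameter.

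**What to change.** **AUC0-last.** Keep it. State in SAP 15.5 and 15.7 that, for the bioequivalence test, it is not estimable when the last quantifiable sample is before Day 85, unless later samples were taken and were below the quantification limit. Alternatively, under the same condition, compute the area to a fixed 98 × 24 = 2,352 h. List every participant's AUC0-last in either case.

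**Partial areas.** Compute AUC29days to 28 × 24 = 672 h and AUC57days to 56 × 24 = 1,344 h, by interpolation with the partial-area setting of the NCA software. This removes only about ±3% noise per participant.

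**Cost.** SAP wording and a software setting, to be agreed before unblinding. A few early leavers will have no AUCt value in the test. For those who leave around Day 57 to Day 71 this gives up a little power (for two Day 57 leavers per arm, 86.8% to 85.2%) in return for a common interval. They keep AUC0-inf where it is estimable.

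### SAP 15.5 divides by AUC0-t in the AUC%extrap formula, so the values would overstate the extrapolated share if the formula is applied as printed

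*SAP*

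**What the plan says.** The parameter table in SAP Section 15.5 describes AUC%extrap in words as "The percentage of the AUC that has been extrapolated beyond the last" observed data point. The formula in the same cell is, in plain notation, (AUC0-inf - AUC0-t) / AUC0-t x 100.

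The AUC0-inf entry in that table gives AUC0-inf as AUC0-t plus an extrapolated tail: the predicted concentration at the last measurable time divided by the terminal rate constant.

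The section also says that the parameters will "be determined from the plasma concentration of palivizumab by non-compartmental analysis using Phoenix WinNonlin". It does not say whether the software's value or the printed expression prevails if they differ. Section 15.3 adds: "Calculated PK parameters will be listed and summarized descriptively". AUC%extrap stands in the parameter table and so falls under that sentence.

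Nothing elsewhere corrects the formula. Protocol Section 13.6.2 gives no expression for AUC%extrap, and SAP Section 18 lists no changes to the planned analysis.

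**The concern.** The words and the formula describe different quantities. A percentage of the AUC that has been extrapolated must refer to an AUC that contains an extrapolated part. That is AUC0-inf; AUC0-t contains none. The printed formula is the ratio of tail to observed area. It exceeds the share for every profile with a non-zero tail, and it passes 100% once more than half of the area is extrapolated, which a share of a whole cannot do.

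AUC0-inf is a primary endpoint, and AUC%extrap is the tabulated measure of how far that endpoint rests on the fitted tail. Values computed as printed would enter the listings and summary tables under a definition they do not meet, and a reader would think AUC0-inf depends more on extrapolation than it does. The distortion is largest for truncated profiles, where the diagnostic is most useful. Such profiles can be analysed: SAP Section 5.3 keeps as PK evaluable those subjects who miss scheduled samples but have enough data points, and Section 15 bases the PK parameters on that set.

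**Working it through.** The documents state no numerical AUC%extrap, so there is no figure of the plan's own to reproduce. The check is algebra, followed by an illustration on the trial's schedule.

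**Algebra.** From SAP 15.5, AUC0-inf = AUC0-t + tail. Let x = tail / AUC0-inf be the true extrapolated share. Then AUC0-t = (1 - x) AUC0-inf, and

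- quantity described in words: 100 x
- quantity printed: 100 x tail / AUC0-t = 100 x/(1 - x)
- printed divided by described: 1/(1 - x) = AUC0-inf / AUC0-t, which is above 1 whenever anything is extrapolated.

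| True share | Value from printed formula | Excess (points) |
|---|---|---|
| 5% | 5.3% | 0.3 |
| 10% | 11.1% | 1.1 |
| 20% | 25.0% | 5.0 |
| 30% | 42.9% | 12.9 |
| 50% | 100% | 50.0 |
| 60% | 150% | 90.0 |

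**Illustration on the schedule.**

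- Sampling times come from Protocol Appendix 2, as elapsed days: 0, 0.17, 0.5, 1, 2, 3, 4, 5, 7, 14, 21, 28, 35, 42, 56, 70, 84, 98. SAP 15.5 confirms that "the PK samples from pre-dose to Day 99 will be considered", so the last sample is 98 days after dosing.
- Assumed, because the documents give neither: a one-compartment model with first-order absorption, C(t) proportional to exp(-kt) - exp(-ka t), terminal half-life 15, 20, 25, 30 or 40 days, and ka 0.3, 0.5 or 1.0 per day.
- Calculation: linear trapezoidal AUC0-t, terminal slope from the last three points, tail = predicted last concentration / slope.

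| Last sample | Tail / AUC0-inf | Tail / AUC0-t (as printed) | Largest gap |
|---|---|---|---|
| Day 99 | 1.1% to 19.4% | 1.1% to 24.1% | 4.7 points |
| Day 71 | 4.1% to 31.6% | 4.3% to 46.2% | 14.6 points |

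The largest gaps occur at the 40-day half-life with ka 0.3 per day. At 25 days with the same ka, the values are 7.28% against 7.85% to Day 99 (gap 0.57 points) and 15.84% against 18.81% to Day 71 (gap 2.98 points, from unrounded values).

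**Cross-check in closed form.** With exact areas and an assumed absorption half-life of 1.5 days, sampling to 98 days gives 1.20% against 1.21% at a 15-day half-life and 19.01% against 23.48% at 40 days. If the last measurable sample is at 56 days, the 40-day case gives 39.37% against 64.93%.

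**The case against.** **The denominator may be a transcription fault.** The point rests on one subscript in a formula extracted from a PDF. The neighbouring AUC0-inf formula shows lambda with an infinity subscript where the text beneath it refers to lambda-z, and it drops the prime on the predicted concentration. Whether these are extraction faults or typing errors in the SAP cannot be told from the extracted text. This stands as a reason to look at the original page before changing anything. Against it, the numerator of the same formula separates 0-infinity from 0-t cleanly, and the CL/F formula shows AUC0-infinity correctly as a denominator.

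**The largest gaps come from profiles the SAP might not report.** SAP 15.5 lists a regression interval shorter than one half-life among the signs that AUC0-inf should not be reported. Three points spanning 28 days cover only 0.70 of a 40-day half-life and 0.93 of a 30-day one. On a three-point window only the 15-, 20- and 25-day cases pass, and the largest gaps fall to 0.57 and 2.98 points. However, the SAP does not limit the regression to three points. At a 40-day half-life, four points to Day 99 (elapsed days 56 to 98) or five points to Day 71 (elapsed days 28 to 70) span 42/40 = 1.05 half-lives. Both satisfy the criterion and give the same 4.7- and 14.6-point gaps. The criteria are also subject to case-by-case review.

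**The practical effect is slight.** The software may never use the printed expression. AUC%extrap is neither a protocol endpoint nor a bioequivalence parameter, and no threshold depends on it. AUC0-last is analysed alongside AUC0-inf. Because x/(1-x) is monotone, participants keep their rank order, and the correct share can be recovered from the listed AUC0-inf and AUC0-last. All of this stands. It limits the importance of the error but does not reconcile the formula with its definition.

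**Conclusion.** The formula, as the SAP text shows it, contradicts the definition beside it and overstates the extrapolated share by the factor AUC0-inf/AUC0-t. That result is exact and needs no assumption. The sizes on this trial's schedule (at most 4.7 points with sampling to Day 99 and 14.6 points when sampling ends at Day 71) rest on the assumed model, half-lives and absorption rates. They are small for complete profiles with shorter half-lives.

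The consequence is limited to the listed and summarised AUC%extrap values, and arises only if the printed expression is the one applied. AUC0-inf, the geometric mean ratios, the 90% confidence intervals and the bioequivalence conclusions do not change. This is a correction the SAP should carry because the parameter is reported. It is not a threat to the primary analysis.

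**What to change.** Check the denominator on the original SAP page. If it reads AUC0-t, change the formula to AUC%extrap = (AUC0-inf - AUC0-t) / AUC0-inf x 100. Add a sentence saying that the reported value is the Phoenix WinNonlin output, and confirm that this output uses the same definition. While on that page, check the subscript of lambda in the AUC0-inf formula as well.

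The cost is one symbol and one sentence. Data collection, sample size and the primary analysis are untouched. If tables have already been produced from the printed formula, the values can be recomputed from the listed AUC0-inf and AUC0-last as 100 x (1 - AUC0-last / AUC0-inf).
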